4.3. Derived and Transformed Data

4.3.1. Baseline Age

The reference date for age is the date of Screening informed consent. Age is calculated as the (reference date – date of birth +1)/365.25 round down to the nearest integer.

4.3.2. Study Day

Study day 1 is defined as the treatment start date. Study day is calculated as:

- Date of interest – treatment start date + 1, if the assessment was performed on or after the treatment start date;
- Date of interest – treatment start date, if the assessment was performed prior to the treatment start date.

There is no safety study Day 0.

4.3.3. Duration:

- Duration in days: (End Date – Start Date + 1)
- Duration in weeks: (End Date – Start Date + 1) / 7
- Duration in months: (End Date – Start Date + 1) / 30.4375; Average days in months = average number of days in a year / 12
- Duration in years: (End Date – Start Date + 1) / 365.25; Average days in a year = 365.25, reflecting the Julian Year of 3 years with 365 days each and 1 leap year of 366 days.

4.3.4. Change from Baseline

Change from baseline is calculated as (visit value – baseline value).

Percent change from baseline is calculated as (change from baseline/baseline value) x 100 when baseline value is not 0.

Post / pre ratio is calculated as Visit value / baseline value when baseline value is not 0.

If either the baseline value or visit value is missing, the change from baseline and/or percent change from baseline is set to missing as well.

Schedule and unscheduled visits post baseline: unless otherwise specified, for the summary by visit post baseline, only scheduled visits will be included; for summary of the maximum or maximum changes post baseline, all scheduled visits and unscheduled visits will be included. All records (scheduled/unscheduled) regardless post baseline reporting period or not will be listed in the data listings.

4.4. Handling of Missing Data

For the patient data listings, no imputation of incomplete dates will be applied. The listings will present the incomplete dates without any change.

4.4.1. Missing or Partial Death Dates

When the death is missing or is partial, it will be imputed based on the last contact date.

- If the entire date is missing, the death date will be imputed as the day after the date of last contact.
- If the day or both day and month is missing, the death date will be imputed to the maximum date among the following dates:
 - 1 day after the date of last contact;
 - 1st day of the month and year of death, if day of death is missing OR
 - January 1st of the year of death, if both the day and month of death are missing.

4.4.2. Missing or Partial Dates in Adverse Events

Every effort will be made to avoid missing/partial adverse event dates in on-study data.

Adverse events with start date that is completely or partially missing will be imputed as follows:

- If the start date has month and year but day is missing, the first day of the month will be imputed;
 - If this date is earlier than the first dose date, then the first dose date will be used instead;
 - If this date is later than the stop date (possibly imputed), then the stop date will be used instead.
- If the start date has year, but day and month are missing, the 15th of June will be imputed:
 - If this date is earlier than the first dose date, then the first dose date will be used instead;
 - If this date is later than the stop date (possibly imputed), then the stop date will be used instead.

If the start date of an event is completely missing, then it is imputed with the first dose date.

Adverse events with stop dates that are completely or partially missing will be imputed as follows:

- If the stop date has month and year but day is missing, the last day of the month will be imputed;
- If the stop date has year, but day and month are missing, the 31th of December will be imputed.

After the imputation, the imputed dates will be compared against the date of death, if available. If the date is later than the date of death, the date of death will be used as the imputed date instead.

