5.4.1. Adverse Events

Treatment-Emergent Adverse Events

An AE will be regarded as treatment-emergent, if

- it occurs for the first time on or after the first dose date of either DSP-7888 or CPI up to 30 days after the last dose of study drug; or
- it occurs up to any time if serious and considered related to study drug.

The emphasis for AE analysis will be based on treatment-emergent AE (TEAE), however all AEs will be listed.

All AEs will be coded using Medical Dictionary for Regulatory Activities (MedDRA version 20.0) and summarized by MedDRA System Organ Class and Preferred Term. The severity of all AEs will be graded by the Investigator using NCI CTCAE version 4.0.

An overview of treatment-emergent adverse events (TEAEs) will be provided. The number and percentage of subjects with following will be summarized for phase 1b, Arm 1 and Arm2 overall, phase 2: CPS < 10, CPS \geq 10 and Overall.

- Subjects with any TEAE
- Subjects with TEAE of CTCAE grade 3 or higher
- Subjects with serious adverse events (all causality and related)
- TEAEs related to study drug
- TEAEs related to study drug with CTCAE grade 3 or higher
- Subjects with TEAE leading to study drug discontinuation (all causality and related)
- Subjects with TEAE leading to study drug dose reduction (all causality and related)
- Subjects with TEAE leading to study drug dose interruption (all causality and related)

Summary of AEs by SOC and Preferred Term

The number and percentage of subjects with TEAEs by SOC, PT and maximum CTCAE grade will be summarized. A summary of TEAEs of CTCAE grade 3 or higher (Grade 3, 4, 5) will be presented by SOC and PT and maximum CTCAE grade (All Grade, \geq Grade 3).

The number and percentage of patients who experience any TEAE will be summarized by SOC and PT (All Grade, \geq Grade 3). A summary of TEAEs by PT and maximum CTCAE grade will be presented. The most commonly reported TEAEs using a different cutoff (e.g. 2% or 10% or more of patients in either arm) may also be summarized by PT as needed.

TEAEs associated with permanent discontinuation /dose reduction/drug interruption of either DSP7888 and/or CPI will be summarized by SOC and PT and maximum CTCAE Grade (taking into consideration the action taken from CRF AE page).

Treatment Related Adverse Events

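### The SAP's rule for partial AE start dates ignores the known month or year: some unresolved pre-dose AEs become TEAEs, and some year-only AEs fall outside the TEAE window

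*SAP*

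**What the plan says.** SAP 4.4.2 gives two start rules. For a missing day: "If the start date has month and year but day is missing, the first day of the month will be imputed". For a missing day and month: "If the start date has year, but day and month are missing, the 15th of June will be imputed". Both carry the same override, "If this date is earlier than the first dose date, then the first dose date will be used instead", and then the same cap, "If this date is later than the stop date (possibly imputed), then the stop date will be used instead". A completely missing start is set to the first dose date.

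Stop dates with the day missing go to the end of the month. For year-only stops, "If the stop date has year, but day and month are missing, the 31th of December will be imputed". No rule is given for a completely missing stop date. Finally, imputed dates are limited by death: "If the date is later than the date of death, the date of death will be used as the imputed date instead".

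SAP 5.4.1 counts an AE as treatment-emergent (TEAE) if it first occurs "on or after the first dose date of either DSP-7888 or CPI up to 30 days after the last dose of study drug". A second limb keeps serious, related events with no time limit.

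Three other passages bear on this:
- SAP 4.4.3, the neighbouring rule for concomitant medications, compares the known month and year with those of first dose.
- SAP 4.4 keeps incomplete dates unaltered in the listings.
- Protocol 12.1.3 allows imputation only for concomitant medication dates.

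**The concern.** Moving an ambiguous start to the first dose date is a normal conservative convention when the known month is the month of first dose. SAP 4.4.2 applies it even when the recorded month or year rules out an on-treatment start. The database will contain such events, because AEs are collected from the main consent (Protocol 6.1.4.4) and screening may run up to 28 days before Cycle 1 Day 1 (Protocol 6.1.4.3).

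The 15 June rule can err the other way. It can place an event that may have begun on treatment after the window has closed. Routine AE collection stops 30 days after last dose, so for most AEs that would be a date on which they could not have been recorded. The result is also incoherent: an AE with no start date at all is kept as a TEAE, while one whose year is known can be lost.

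SAP 5 limits the final report to safety, and SAP 5.4.1 rests the AE analysis on TEAEs. Misclassified events would affect the incidence tables, the Phase 1b summary of AEs between consent and first dose (Protocol synopsis), and time to first injection site reaction (ISR).

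**Working it through.** There is no plan figure to reproduce. The check applies the SAP 4.4.2 rules in the order written, then the SAP 5.4.1 window.

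**Worked dates**

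| Recorded start | Stop | Dosing | Imputed start | TEAE? |
|---|---|---|---|---|
| Mar 2021 | ongoing, or 20 Apr 2021 | from 10 Apr 2021 | 10 Apr 2021 | yes, although onset was in March |
| Mar 2021 | Apr 2021, day missing (becomes 30 Apr) | from 10 Apr 2021 | 10 Apr 2021 | yes |
| Mar 2021 | 5 Apr 2021 | from 10 Apr 2021 | 5 Apr 2021 | no; the stop-date cap protects it |
| 2020 | ongoing | from 15 Jan 2021 | 15 Jan 2021 | yes, although onset was in 2020 |
| 2021 | missing, or 2021 (becomes 31 Dec) | 11 Jan to 22 Mar 2021 | 15 Jun 2021 | no; window closed 21 Apr |
| 2021 | 30 Mar 2021 | 11 Jan to 22 Mar 2021 | 30 Mar 2021 | yes; capped |
| 2021 | ongoing | 1 Sep 2020 to 22 Mar 2021 | 15 Jun 2021 | no; window closed 21 Apr |

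The third row depends on applying the stop-date cap to the date after the override. If the cap is tested on the date before the override, the start becomes 10 Apr 2021, after the event's own stop date, and the event is a TEAE.

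**Error 1: how often a pre-dose AE carries an earlier month**

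Assume first doses spread evenly over a 365-day year and onset spread evenly over the n days from consent to first dose (n at most 28). For a first dose on day d of a month, with d no greater than n, n − d + 1 of those days lie in an earlier month. Summing over d gives n(n+1)/2 per month, so

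share = 12 × n(n+1)/2 ÷ (365n) = 6(n+1)/365.

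- n = 7: 48/365 = 13%
- n = 14: 90/365 = 25%
- n = 21: 132/365 = 36%
- n = 28: 174/365 = 48%

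Of these, all that are unresolved at first dose become TEAEs. The year-only branch needs a start in the previous calendar year: (n+1)/730, or 29/730 = 4% at n = 28.

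**Error 2: how often 15 June falls after the window**

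Let f be the day of the year of first dose and D the study day of last dose. The window closes on day f + D + 29, and 15 June is day 166. Considering AEs dated to the first-dose year only, the window has closed when f ≤ 136 − D. The share of first-dose dates is (136 − D)/365:

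- D = 22: 114/365 = 31%
- D = 64: 72/365 = 20%
- D = 85: 51/365 = 14%
- D = 127: 9/365 = 2.5%
- D = 169: none

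Treatment that crosses New Year adds to this. Take true TEAEs with onset uniform over the D + 30 window days, only the year known, and no stop or death cap. For D up to 136, windows that cross New Year place 1, 2, …, D + 29 days in the next year, all lost. Then

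share lost = [(136 − D) + (D + 29)/2]/365.

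- D = 22: (114 + 25.5)/365 = 38%
- D = 85: (51 + 57)/365 = 30%
- D = 169: the first term is zero, and next-year days are lost only while there are at most 165 of them: (1 + … + 165)/(365 × 199) = 13,695/72,635 = 19%

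**The case against.** The strongest reply is that the cases needed are rare and partly protected.

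- Required on-treatment visits are 1 to 3 weeks apart, AEs are reviewed at each (Protocol 11.1.2.2.1), missing data are queried (Protocol 16.2), and SAP 4.4.2 itself commits to avoiding partial dates. A year-only start should be uncommon. This stands and limits the impact.
- A known stop before first dose, with the cap applied after the override, keeps a resolved event pre-dose. Error 2 disappears if an earlier stop or death date pulls the start back into the window. Serious, related events stay in under the second TEAE limb. All of this stands.
- Error 1 over-counts TEAEs, which is the cautious direction for safety. That is true, but error 2 goes the other way, so the rule is not consistently conservative.
- Unaltered dates remain in the listings, so affected cases can be seen. Listings do not correct the incidence tables.
- Protocol 12.1 lets the SAP modify protocol plans. That may explain imputing AE dates despite Protocol 12.1.3, but the two texts still disagree.

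A reader might infer that every AE predating dosing becomes a TEAE, or that nearly half of screening AEs do. The documents do not support that: the 48% applies only to AEs with the day missing, assumes the full 28 days that the protocol sets as a maximum, and matters only for events unresolved at first dose. A reader might also take the error 2 percentages as a share of all TEAEs. They are shares of first-dose dates, or of uncapped year-only events, at treatment durations that the documents do not give.

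**Conclusion.** The defect holds in this form. SAP 4.4.2 disregards the known part of a partial AE start date, and nothing else in the SAP corrects the result.

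1. An AE recorded in a month or year wholly before first dose becomes a TEAE if it is ongoing at first dose, ends after it, or has a stop date imputed after it.
2. A year-only AE leaves the TEAE tables if last dose plus 30 days falls before 15 June of the recorded year, no earlier stop or death date applies, and it is not both serious and related. Treatment crossing New Year is included.

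The ranges (13% to 48% for error 1; 31% to 0% of first-dose dates, or 38% to 19% of uncapped year-only TEAEs, for error 2) rest on uniform dates, 7 to 28 days from consent to dosing, and last dose between Day 22 and Day 169. All of these are assumptions. The number of partial dates is unknown and probably small, so the documents do not show that the safety conclusions would change. The reason to act is that a stated rule misclassifies events in the tables that carry a safety-only report, and correcting it is cheap.

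**What to change.** Reword the start-date part of SAP 4.4.2:

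- If the known month and year (or the known year, for year-only dates) equal those of first dose, impute the first dose date.
- If the known period is earlier, keep the event as pre-dose.
- If it is later, impute the 1st of the month, or 1 January for a year-only date.
- Apply the stop-date and death caps after these steps, and say so.
- Delete the 15 June rule.

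With this rule, the unresolved pre-dose examples in the table stay pre-dose. The three year-only 2021 examples are TEAEs, with starts of 11 January, 11 January and 1 January 2021. Repeating the enumerations with the revised rule brings both misclassification rates to zero.

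The cost is SAP wording and the matching derivation code; no new data are needed. There is one small downside: a year-only ISR start set to first dose gives the shortest possible time to first ISR. Report how many AE and ISR onset dates were imputed. In the same revision, reconcile SAP 4.4.2 with Protocol 12.1.3, for example by stating in the SAP that AE date imputation departs from the protocol text.

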4.4.3. Missing or Partial Dates in Concomitant Medications

Every effort will be made to avoid missing/partial concomitant medication dates in on-study data. Concomitant medication with start dates that are completely or partially missing will be analyzed as follows to be included as Concomitant Medications summary tables :

- If the start date has month and year but day is missing, the medication will be included in the summary table if the month and year of the start date of the event are:
 - On or after the month and year of the date of the first dose of study drug and
 - On or before the month and year of the date of the last dose of study drug plus 30 days.
- If the start date has year, but day and month are missing, the therapy will be included in the summary table if the year of the start date of the event is:
 - On or after the year of the date of the first dose of study drug and
 - On or before the year of the date of the last dose of study drug plus 30 days.

If the start date of an event is completely missing, then the therapy will be included in the summary table.

4.4.4. Missing or Partial New Anti-Cancer Therapy Start Date

Post treatment anti-cancer therapy and radiotherapy start dates may be imputed to determine date of new anti-cancer therapy.

Incomplete dates for start date of new anti-cancer therapy will be imputed as follows and will be used for determining censoring dates for efficacy analyses.

- The end date of new anti-cancer therapy will be included in the imputations for start date of new anti-cancer therapy. If the end date of new anti-cancer therapy is
 - completely missing then it will be ignored in the imputations below;
 - partially missing with only year (YYYY) available then the imputations below will consider 31DECYYYY as the end date of the new anti-cancer therapy;
 - partially missing with only month and year available then the imputations below will consider the last day of the month for MMMYYYY as the end date of the new anti-cancer therapy.
- For patients who have not discontinued study drug at the analysis cutoff date, last dose of study drug is set to the analysis cutoff date is the imputations below
- *If the start date of new anti-cancer therapy is completely or partially missing, the imputed start date of new anti-cancer therapy is:*
 - = 31DECYYYY, if only Year is available and $Year < Year\ of\ min\ [max(PD\ date + 1, last\ dose\ of\ study\ drug + 1), end\ date\ of\ new\ anti-cancer\ therapy]$
 - = Last day of the month, if both Year and Month are available and
 - $Year = Year\ of\ min\ [max(PD\ date + 1, last\ dose\ of\ study\ drug + 1), end\ date\ of\ new\ anti-cancer\ therapy]$
 - $Month < Month\ of\ min\ [max(PD\ date + 1\ day, last\ dose\ of\ study\ drug + 1\ day), end\ date\ of\ new\ anti-cancer\ therapy]$
 - = $min\ [max(PD\ date + 1, last\ dose\ of\ study\ drug + 1), end\ date\ of\ new\ anti-cancer\ therapy]$, for all other cases.

5. STATISTICAL METHODOLOGY AND STATISTICAL ANALYSES

As the study was terminated for phase 2 portion due to the interim monitoring for efficacy. The final CSR will focus on the safety updates for the study as a synoptic CSR. As a result, the analyses strategy will focus on the safety portion. No analysis for efficacy and PD/biomarker are included for the final CSR.

Whilst every effort has been made to pre-specify all analyses in this statistical analysis plan, if any additional exploratory analyses be found to be necessary, the analyses and the reasons for them will be detailed in the clinical study report (CSR).

5.1. General Statistical Methods

5.1.1. Analysis for Continuous Data

Descriptive statistics, including the mean, standard deviation, median, minimum and maximum values will be provided for continuous endpoints.

5.1.2. Analysis for Categorical Data

The number and percentage of patients in each category will be provided for categorical variables. Change from baseline for Categorical data will be evaluated by shift table if appropriate.

5.2. Standard Analysis

5.2.1. Subjects Disposition

All patients who signed pre-screened and screened informed consent will be summarized. The number and percentage of study patients will be tabulated for different analysis sets (Section 3) and by different phases and treatment information below.

Phase 1b: Arm 1, Arm 2; Overall,

Phase 2: CPS < 10, CPS >= 10, Overall

The number and percentage of patients reaching end of treatment, and end of study, along with the discontinuation reasons will be summarized as treatment assignment in phase 1b and CPS subgroups and overall in phase 2.

Listing for analysis sets and end of treatment and end of study reasons will be provided.

5.2.2. Demographic and Baseline Characteristics

The following demographic and baseline characteristics will be summarized.

- Age, Age group (< 65 years and >= 65 years), sex, race, ethnicity, ECOG status, and smoking history, HLA type, CPS score, and CA-125 (for phase 2 only).
- Weight (kg), height (cm), body mass index (BMI).

Demographic and baseline characteristics will also be listed for each patient.

5.2.3. Disease Characteristics, Cancer History and Prior Cancer treatment

Disease characteristics including, but not limited to, cancer type, cancer history, prior cancer therapy, baseline tumor burden will be summarized:

- Cancer type
- Duration of Last Cancer Therapy in weeks: calculated by $(\text{end date} - \text{start date} + 1) / 7$ from last cancer therapy, Status of patient entering study in regarding to the last therapy.
- Number of prior therapy (1,2, ≥ 3).
- Prior Bevacizumab (only for phase 2 part):
- Prior cancer system medication (Yes vs No); the number and percentage of patients with each preferred base, best response from prior cancer system medication will be summarized. If multiple best responses are reported, the best one is reported.
- Prior Radiotherapy: prior radiotherapy (Yes, No), time (months) since Stop Date of Radiation Therapy to the first dose date(Computed as $[(\text{first dose date}) - (\text{stop date of radiation therapy}) + 1] / 30.4375$), Number of Fractions and Total Dose (Gy) per person, best response from prior cancer radiotherapy will be summarized. If multiple best responses are reported, the best one is reported.
- Prior Cancer Surgery (Yes , No) and by SOC and Preferred Terms of Medical Dictionary for Regulatory Activities (MedDRA 20.0).
- Tumor Burden: Sum of Product of Diameters of Target Lesion (mm²), Site of Target Lesion

5.2.4. Prior and Concomitant Medications

Prior and concomitant medications will be coded to ATC (Anatomical Therapeutic Chemical) classification and Drug Name using WHODrug Dictionary (WHO-DD-B2) version June 2017.

Medications that start and stop prior to the date of first treatment administration (either DSP-7888 or checkpoint inhibitor (CPI) whichever is administrated first) will be classified as ‘prior’ medications. If a medication starts on or after the date of first treatment administration, then the medication will be classified as ‘concomitant’. If a medication starts before the date of first treatment administration and stops on or after the date of first treatment administration, then the medication will be categorized as both a ‘prior’ and ‘concomitant’ medication.

Prior and concomitant medications will be listed for the safety analysis set.

5.2.5. Medical History

Medical history will be coded using MedDRA v20.0. Medical history will be listed.

5.2.6. Extent of Exposure

Dose Schedule for phase 1b part is summarized as below:

Table 5: Phase 1b Study Dose Level and Schedule

DSP-7888 Dosing Emulsion Dose Level	DSP-7888 Dosing Emulsion Dose and Schedule
DSP-7888 Dosing Emulsion Dose Level I	Nivolumab Arm (Arm 1): 10.5 mg weekly for 4 weeks for induction phase, then every 2 weeks for maintenance phase Pembrolizumab Arm (Arm 2): 10.5 mg weekly for 3 weeks for induction phase, then every 3 weeks for maintenance phase
DSP-7888 Dosing Emulsion Dose Level II	Nivolumab Arm (Arm 1): 3.5 mg weekly for 4 weeks for induction phase, then every 2 weeks for maintenance phase Pembrolizumab Arm (Arm 2): 3.5 mg weekly for 3 weeks for induction phase, then every 3 weeks for maintenance phase
DSP-7888 Dosing Emulsion Dose Level III	Nivolumab Arm (Arm 1): 1.75 mg weekly for 4 weeks for induction phase, then every 2 weeks for maintenance phase Pembrolizumab Arm (Arm 2): 1.75 mg weekly for 3 weeks for induction phase, then every 3 weeks for maintenance phase

Table 6: PD-1 Inhibitor Dose

PD1 Inhibitor	Dose and Schedule
Nivolumab	In Arm 1, 240 mg administered intravenously (IV) over 30 minutes (± 5)* every 14 days (2 weeks/cycle) starting from Day 1 of Cycle 3 (Day 29), then maintenance phase (after Cycle 3).
Pembrolizumab	In Arm 2, 200 mg/8 mL administered through IV infusion over 30 (± 5) minutes every 21 days (3 weeks) starting from Day 1 of Cycle 2 (Day 22), then maintenance phase (after Cycle 2).

*The administration time change from 60 to 30 minutes is based on the updated dosage and administration guidance of the new nivolumab product label released in July 2018.

DSP-7888 Dosing Emulsion and pembrolizumab will be administered at the recommended dose level from the Phase 1 part of the study, following the same schedule as listed in Table 10.

Table 7: Phase 2 Study Dosing Schedule

Investigational Product	Frequency	Dosage	Route of Administration
DSP-7888 Dosing Emulsion	Q1W for first 3 weeks Q3W post 3 weeks	10.5mg	Intradermal injection (ID)
Pembrolizumab	Q3W, starting from Day 1 of Cycle 2 (Day 22)	Solution for infusion 200mg/8mL	IV infusion

The dose schedules for the study have been changed under different protocol amendment. Below is a summary of the different dosing schedule:

Table 8: Planned Dose Intensity

Treatment Group	Dose Level	During Induction Phase	During Maintenance Phase
DSP-7888 Dosing Emulsion + nivolumab	Level I (10.5 mg)	10.5 mg / week	5.25 mg / week
	Level II (3.5 mg)	3.5 mg / week	1.75 mg / week
	Level III (1.75 mg)	1.75 mg / week	0.875 mg / week
DSP-7888 Dosing Emulsion + pembrolizumab	Level I (10.5 mg)	10.5 mg / week	3.5 mg / week
	Level II (3.5 mg)	3.5 mg / week	1.17 mg / week
	Level III (1.75 mg)	1.75 mg / week	0.58 mg / week

In Phase 2, the dose of DSP-7888 Dosing Emulsion will be the recommended dose, as determined in the Phase 1b Arm 2 part (DSP-7888 + pembrolizumab) of the study

Figure 1: Dose Schedule Summary.

	induction				maintenance											
102CI-NIV	1	8	15	22	29	36	43	50	57	64	71	78	85	92	99	106
DSP7888	x	x	x	x	x		x		x		x		x		x	
NIVO	x		x		x		x		x		x		x		x	

102CI-NIV	1	8	15	22	29	36	43	50	57	64	71	78	85	92	99	106
DSP7888	x	x	x	x	x		x		x		x		x		x	
NIVO					x		x		x		x		x		x	

102CI-PEM	1	8	15	22	29	36	43	50	57	64	71	78	85	92	99	106
DSP7888	x	x	x	x	x	x	x			x			x			x
PEM	x			x			x			x			x			x

102CI-PEM	1	8	15	22	29	36	43	50	57	64	71	78	85	92	99	106
DSP7888	x	x	x	x			x			x			x			x
PEM				x			x			x			x			x

Duration of exposure (i.e., weeks on study drug) will be calculated as the number of weeks from first to last dose date, (last exposure date - first exposure date + 1)/7.

The number of patients with a dose reduction or dose interruption in each dose group or treatment group will also be summarized.

